12.6 Adverse Reactions/Side Effects

Azithromycin is generally well-tolerated. The most common side effects of azithromycin are diarrhea, nausea, abdominal pain, and vomiting, each of which may occur in fewer than one in twenty persons who receive azithromycin. Rarer side effects include abnormal liver function tests, allergic reactions, and nervousness. Diarrhea due to *Clostridium difficile* has been reported in rare cases.

During the consent process, the common adverse reactions that may occur will be explained to parents/guardians and they will be advised to communicate adverse events to CRSN study staff immediately. If, for any reason, the participant needs further care, they will be referred to the nearest health center for examination and treatment.

The trial sites will be masked to outcomes, so the responsibility for monitoring interim analysis will fall on the DSMC. Statistical monitoring is discussed in the Statistical Analysis Plan. The Data Safety and Monitoring Committee (DSMC) will be given authority to discontinue treatments at any time if there is evidence of unexpected harm.

12.7 Adverse Events Systems

Both active and passive monitoring systems for adverse events are in place for this study, and these monitoring activities will specifically include (but will not be limited to) treated 1-6 month olds. We will monitor adverse events following mass treatments actively at each follow-up census and during a house-to-house survey of all 1-6 month olds in a random selection of azithromycin and control communities.

12.7.1 Passive Adverse Events Monitoring

We will implement a passive monitoring system during the treatment phase, by instructing parents to report any adverse events in the two weeks following each mass azithromycin distribution to a local healthcare provider. Children will be referred for follow up care on a case-by-case basis.

12.7.2 Active Adverse Events Monitoring

Infant Adverse Events Survey

To identify any adverse events associated with mass treatment, the research team will randomly select 48 study communities (12 per arm) to participate in an adverse events survey. This survey will be performed by the census workers masked to treatment arm, approximately 2 weeks after a mass medication distribution during the first phase only (CHAT 0). During the survey, adverse events will be elicited only for study participants aged 1-6 months at the previous census. A structured questionnaire will be performed to elicit dangerous side effects, followed by an open-ended question. Specifically, we will ask the primary caregiver about the following symptoms during the time since the previous antibiotic distribution: abdominal pain, vomiting, diarrhea, constipation, hemorrhoids or rash. We will only collect this infant adverse events survey for the first phase. The rest of the phases of the trial will not collect this information.

Training

The household survey team will be the same individuals who conducted the census. They will be trained in survey administration methods, including:

1. Obtaining informed consent
2. Accurately selecting the appropriate households to interview
3. Remaining neutral when asking questions (i.e. asking the question exactly as it is written on the paper in a neutral tone of voice, so as not to lead the respondent or introduce bias)

Serious Adverse Events

Any serious adverse events (SAE) will be reported to Pfizer. An **IIR SAE Form** (*Investigator-Initiated Research Serious Adverse Events Form*) will be completed for each event. (See Appendix for form and complete instructions.)

According to Pfizer, an SAE is any adverse event that:

- Results in death
- Is life-threatening (i.e., causes an immediate risk of death)
- Requires inpatient hospitalization or prolongation of existing hospitalization
- Results in persistent or significant disability or incapacity
- Results in a congenital anomaly or birth defect

Or that is considered to be:

- An important medical event

All community residents will be advised to alert a village health worker if they experience, within one week of mass treatment, a serious adverse event (by the preceding definition). An SAE report must be submitted for all deaths in the study – regardless of the time of treatment. The local health worker will report to the study coordinator; who must, within 24 hours, submit a Pfizer **IIR SAE Form** to [contact]. AS and TL will review, and forward to Pfizer and/or the Medical Monitor, as appropriate. SAEs must be submitted to Pfizer within 24 hours of receipt from the on-site coordinator. AS and TL will also forward SAE to DSMC if meets criteria of being possibly related to study drug. The reporting of any serious adverse event will follow national procedures in Burkina Faso.

- In the event of serious events, the CSPS will contact the study doctors on the same day. The patient will then be evacuated to an appropriate level of care for management.
- The declaration will be made to the National Agency for Pharmaceutical Regulation in accordance with the regulations and within the deadlines (7 days in the event of death or life-threatening prognosis, 15 days in other serious and unexpected cases, 15 days in new facts) at [contact]
- The ethics committees will also be informed of the occurrence of this event within the same time frame.

Deaths that are reported to the study team outside of the biannual census (primary outcome) will be reported as an SAE to Pfizer. Note that deaths identified via the biannual census, which constitute the primary outcome, will not be reported as SAEs. Deaths that are reported to the study team as part of the biannual census will be reported to Pfizer in aggregate, not by arm, on a quarterly basis.

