5.2.2. Non-core Study Elements

The designation “non-core” element means that not all study communities will be participating in the activity.

Mother MUAC assessment

In a subset of 20 villages, we will train mothers/guardians on measuring MUAC on their children weekly. We will train mothers/guardians to bring children to the nearest CSPS for evaluation if MUAC is <125mm.

Passive Surveillance

In each Centre de Santé et de Promotion Sociale (CSPS, community health facility), we will conduct morbidity passive surveillance. Each CSPS will be equipped with a tablet for electronic capture of health facility visits. Each visit will be recorded, including the reason for the visit (e.g., fever, diarrhea, malnutrition, etc), the village of residence, the person’s age and sex, diagnosis (e.g., malaria, pneumonia, etc), treatment (e.g., antibiotic, antimalarial, etc), and timing of the visit (e.g., first versus follow-up visit). Note that this data is already routinely collected on paper forms. Identifying information like names will not be collected.

In each CSPS included in the Mother MUAC assessment, we will collect data on malnutrition including name of participants in the program, study ID, village of residence, date of admission in the program, measurements of weight and height, treatment received and outcome. Notes that this data is already collected on paper forms

Passive surveillance in the district hospitals located in our study area: we will collect study ID, name of participant, village of residence, date of admission and discharge, reason for hospitalization, treatment, and outcome of hospitalization for all children hospitalized under 6 months of age. Notes that this data is already collected on paper forms

7.1 5.3 Individually randomized targeted treatment

Recruitment

There are three occasions in which children could be recruited for the targeted treatment:

- 1) During the 1st BCG visit at approximately 5 weeks of life if the child is at least 29 days old.
- 2) During the 6 week (42 days) postnatal follow-up visit or any other well-child visit happening during the age of 5 weeks to 12 weeks
- 3) When children are attending their first EPI vaccine visit at approximately 12 weeks of life (1st EPI vaccine visit).

Enrollment

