The children will be enrolled for targeted treatment at the health center or during other health outreach in the community after obtaining written consent from at least one guardian. Enrollment will happen at the Nouna district, the K. Vigué district and Banfora districts

The children enrolled have to be living in a participating study community and be aged 28 days to 12 weeks.

Anthropometric Baseline assessments

All children enrolled in the study will undergo anthropometry: we will measure height, weight and middle arm circumference of each child.

Treatment

In all communities, children attending local health posts or children present at community health outreach will have the opportunity to receive a dose of azithromycin or placebo. Children will be individually randomized to receive placebo or azithromycin. Receipt of treatment will be recorded on the child's study card. This treatment will occur whether the targeted treatment occurs during other health outreach or when the caregiver seeks vaccination at the health post or when the child visits the health post for a well-child visit. Community health workers will conduct a household visit when the mother and child do not come to the health post.

2-week infant adverse event survey

To identify any adverse events associated with the individually treated children, the research team will perform an adverse event survey approximatively 2 weeks after the treatment has been administered in a random subset of children. 10% of the children treated as part of the study will be randomly selected and the 2-week IAES will be performed. This survey will be performed by the census workers masked to treatment arm. A structured questionnaire will be performed to elicit adverse events following treatment, followed by an open-ended question. Specifically, we will ask the primary caregiver about the following

symptoms during the time since the previous antibiotic distribution: abdominal pain, vomiting, diarrhea, constipation, hemorrhoids or rash.

Six-month Mortality

All children treated in all study communities will be followed for 6 months for vital status assessment. At approximately 6 months of age, a field worker will assess the vital status of the child (alive, died, unknown) and their current residence (residing in the household, moved, unknown). This visit will be an in-person visit to the health post.

Six-month Anthropometry assessment

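### The two caregiver reporting windows count only from mass treatment, none is stated for the individually randomised infant dose, and no step passes the under-6-month hospital log into serious adverse event reporting

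*Protocol*

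**What the plan says.** **Windows given to families.** Protocol 12.7.1 sets up passive monitoring by "instructing parents to report any adverse events in the two weeks following each mass azithromycin distribution to a local healthcare provider". The SAE part of 12.7.2 has a one-week alert: "All community residents will be advised to alert a village health worker if they experience, within one week of mass treatment", completed by a reference to an SAE as defined just above it.

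**Who is dosed, and where.** Section 3.1 randomises Nouna communities to biannual mass treatment. It randomises the targeted dose individually in Nouna, K. Vigué and Banfora. Section 5.3 puts that dose at 28 days to 12 weeks of age, at a health post or community outreach.

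**Safety follow-up after the targeted dose.** Section 5.3 states that "10% of the children treated as part of the study will be randomly selected and the 2-week IAES will be performed". The survey lists six symptoms and ends with an open question. At about 6 months of age all treated children have a visit for vital status, residence and anthropometry.

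**Hospital log.** Section 5.2.2, under passive surveillance in district hospitals in the study area, collects study ID, admission and discharge dates, reason, treatment and "outcome of hospitalization for all children hospitalized under 6 months of age".

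**SAE definition and general duty.** In 12.7.2 an adverse event is serious if, among other criteria, it "Requires inpatient hospitalization or prolongation of existing hospitalization". The same section says "Any serious adverse events (SAE) will be reported to Pfizer", with no trigger or time limit.

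**The concern.** Section 12.7 says that the active and passive systems specifically include treated infants of 1 to 6 months. Section 12.7.3 promises separate reporting of side effects in that age group, and section 15.5 puts adverse events by intervention group into the DSMC Closed Reports. All three depend on events being captured.

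The individually dosed infants fall almost entirely within that age group and are among the youngest treated. Yet the rules that tell families when to report were written around mass rounds. They read as text that was not updated when targeted dosing, and later districts, were added.

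What is at stake is the capture of serious non-fatal events, chiefly hospital admissions, by individual arm. The study holds a record of such admissions but does not say that anyone looks at it for safety.

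**Working it through.** The plan gives no figure to reproduce. The check is mainly a comparison of the text, with simple arithmetic for scale.

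**Step 1. Each safety rule, its starting point, and whether it reaches a targeted infant.**

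| Rule | Protocol section | Counted from | Reaches a targeted infant? |
|---|---|---|---|
| Passive adverse event window, 2 weeks | 12.7.1 | mass distribution | only if a mass round happens to coincide |
| SAE alert window, 1 week | 12.7.2 | mass treatment | only if a mass round happens to coincide |
| Infant survey after mass treatment | 12.7.2 | first mass round only | not designed for the targeted dose |
| Advice at consent to report events | 12.6 | no trigger | yes, if the caregiver reports |
| General duty to report SAEs | 12.7.2 | no trigger | yes, once someone knows of the event |
| Same-day contact by the health facility (CSPS) | 12.7.2 | no trigger | yes, if the CSPS knows |
| Deaths rule | 12.7.2 | any time | yes, for deaths |
| 2-week survey | 5.3 | targeted dose | yes, random 10% |
| 6-month visit | 5.3 | age | yes, but not for non-fatal events |
| District hospital log | 5.2.2 | age under 6 months | recorded; no onward step stated |

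**Step 2. Follow one infant.** Take an infant given the targeted dose in Banfora and admitted directly to a district hospital four days later.
- Neither caregiver window is open.
- The consent advice and the general duty apply, but need someone to report or recognise the event.
- The CSPS route works if the CSPS learns of the admission.
- The 2-week survey reaches the family with probability 1 in 10, and the admission would have to come out in the open question.
- The 6-month visit does not ask.
- If the hospital is covered by the log, the admission is on record with study ID and date, but no one is assigned to screen it.

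**Step 3. Coverage of the windows.** Assume one mass round per 182 days and targeted doses spread evenly over time.
- Nouna, chance of any overlap between a 7-day post-dose period and a 7-day mass-round window: (7 + 7)/182 = 7.7%.
- Nouna, average share of the 7-day post-dose period that is covered: 7/182 = 3.8%.
- Nouna, average share covered by the two-week passive window: 14/182 = 7.7%.
- K. Vigué and Banfora: 0, because no mass round is described there.

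**Step 4. Follow-up contact.**
- Without an active adverse event survey: 100% − 10% = 90%.
- Time from the dose to the visit at about 26 weeks of age: 26 − 12 = 14 weeks to 26 − 4 = 22 weeks.

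**Step 5. Illustration only.** The documents give no admission rate. Assume 0.1% to 1% of dosed infants are admitted within two weeks. Per 10,000 dosed:
- Admissions: 10,000 × 0.001 = 10, to 10,000 × 0.01 = 100.
- In surveyed families: 10% of these, or 1 to 10.
- In families not surveyed: 9 to 90.

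**The case against.** The strongest reply is that the protocol does not depend on the two windows. "Any serious adverse events (SAE) will be reported to Pfizer" has no trigger. Deaths are covered separately: "An SAE report must be submitted for all deaths in the study – regardless of the time of treatment". The CSPS must contact study doctors the same day about serious events, and it is the facility closest to where targeted infants are dosed. Caregivers are told at consent to report events immediately. Section 12.7.3 sends all adverse events of azithromycin to the DSMC. The consent pages, the infant survey form and the SAE form guide (Appendices 2 and 3) are not available here and may carry instructions for targeted infants.

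Most of this stands, and it rules out several stronger readings that a reader might infer:

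- *SAE rules begin only with mass treatment.* They do not; four of the rules above have no such trigger.
- *The village or local health worker is the only route.* The CSPS route is separate.
- *Logged admissions never reach SAE reporting.* The step is unspecified, not excluded.
- *90% of these infants have no active safety contact.* All have the 6-month vital status visit; the 90% lack an active adverse event survey.
- *The 2-week survey cannot pick up an admission, or does not reach K. Vigué and Banfora.* It has an open question, and its sample is drawn from all treated children.
- *The DSMC would see few or no admissions.* The documents do not allow that forecast.

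The reply does not close the gap. The general duties apply to an SAE that is already known. They do not tell targeted families over what period to report, and they do not turn the hospital log into reports. If the unseen forms do so, sections 12.7.1 and 12.7.2 still need to agree with them.

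**Conclusion.** The point holds in a limited form. Two caregiver windows of different length are stated, both counted from mass treatment, and neither is given for the individually randomised dose. As worded they cannot open in two of the three targeted-dosing districts, and in Nouna they coincide with the post-dose period only by chance (about 4% average coverage for the one-week window, about 8% for the two-week window). No step is stated from the under-6-month hospital log to SAE review or to the DSMC.

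This is a gap in stated procedure, not evidence that events were missed. It does not affect the mortality analysis. It makes the ascertainment of serious non-fatal events least specified in the youngest individually randomised infants, and it is cheap to close.

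The coverage figures assume even dosing and a 182-day cycle. The 10 to 100 admissions per 10,000 rest on an assumed rate, and the conclusion does not depend on them. The log is a non-core element limited to district hospitals in the study area, and the text does not say whether that includes K. Vigué and Banfora.

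**What to change.** 1. Reconcile 12.7 to 12.7.2 with 5.2.2 and 5.3, so that both caregiver windows count from any study dose, mass or targeted, in all three districts. The text should also say which of the two stated windows governs the linkage in item 2. No particular length is proposed here.
2. State that the data manager periodically links the district hospital log to dose dates on study ID, and sends admissions inside that window to the coordinator for SAE review. Say which hospitals the log covers.
3. Tabulate these admissions in the DSMC Closed Report by individual arm for targeted infants, and by community arm for mass treatment in Nouna.

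Items 2 and 3 use data that the protocol already collects, so they can also be run on existing records. This assumes that the study ID in the log matches the one in the treatment data. The cost is protocol wording, a periodic linkage, and more SAE forms, most of them probably unrelated to study drug.

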12.7.3 Adverse Events Data

We will keep records and report all adverse events of azithromycin to the DSMC. We will report both efficacy and side effects of azithromycin separately for the 1-6 month old age group. For any “sudden deaths” believed to be associated with azithromycin treatment, key informants will immediately notify the verbal autopsy interviewer via SMS message or another appropriate form of rapid communication. Reporting of non-serious adverse events will follow national procedures in Burkina Faso, as well. In the event of a non-serious adverse event, the CSPS will process the cases and the national reporting form will be completed. Any adverse event occurring during the trial will be covered by the study free of charge.

11.2 12.8 Supply issues

If a study site runs out of a treatment letter, a request should be sent to [contact] to request a replacement for the community in question. This is not blanket permission to substitute one letter for another – if there are several communities for which the assigned treatment has run out, a separate request must be made for each community.

The study site coordinator will make the request; TCP will determine the replacement letter, a member of the DCC will make the change(s) in the database.

The field team must log out of the MORDOR mobile app and log in again for the changes to take effect on the front end. The replacement treatment letter will then appear in the app.

12 Chapter 13: Protection of Human Subjects

Before the study begins, the research team will obtain formal ethical approval from their respective ethics committees as well as national ethical approval in Burkina Faso. In addition, staff will approach community leaders to describe the study and answer any questions. Study staff will proceed only if local leadership consents to participate. Verbal consent will be collected from the village leadership. We will also obtain verbal consent from the head of household to be able to perform the census. To be able to examine and treat the children living in the household, we will obtain written informed consent from a parent or guardian. This written consent will contain information regarding all study activities with patient contact: examinations, and treatments. We will collect one written consent form per child the first time we enroll the child. The subsequent visits we will explain the study to the parent/guardian of the child but we will only obtain verbal consent. Children will be included in the study only following the receipt of the written consent from a parent or guardian. If, at any time, a parent or guardian elects to withdraw a family member from the study, they will be free to do so. Individuals who withdraw will be offered the same medical treatment outside the study.

Children with wasting, stunting, malaria, or anemia will be referred for appropriate treatment by trained study personnel, at the nearest health center.

13.1 Institutional Review Board Approval

UCSF Committee on Human Research

UCSF's Committee on Human Research will annually review study protocol for ethical approval.

CRSN Comité Institutionnel d'Ethique

The study protocol will be reviewed and granted ethical approval by the Comité Institutionnel d'Ethique at the CRSN headquarters before any patient-related research activities begin.

National Health Ethics Committee of Burkina Faso.

The study protocol will be reviewed and granted ethical approval by the National Health Ethics Committee of Burkina Faso before any patient-related research activities begin and annually.

13.2 Informed Consent

First, the chairman of each village will be asked for permission to include the village in the study. Additionally, the study will be discussed with all adults in the village by team members who speak the local language(s).

Informed consent scripts will be translated into local languages before the study can begin. Consent scripts will then be back-translated by a different party to ensure comprehension. Consent scripts will be submitted and approved by national IRB committees in Burkina Faso prior to study implementation. Then they will be read aloud to each study participant (and his/her parent/guardian) by a team member who is a native speaker of the local language to ensure that they understand the risks and benefits of participating in all study activities. Young adults and children under 18 years of age, who cannot give consent by law, will be included in the study only following the receipt of written informed consent from a parent or guardian. If, at any time, a parent or guardian elects to withdraw themselves or a family member from the study, it will be made clear that they will still be eligible for treatment.

